5.3 Lifestyle Considerations

No other restrictions than the ones listed in the exclusion criteria or in the contraindications for subsequent vaccinations are required.

5.4 Screen Failures

Screen failures are defined as participants who consent to participate in the clinical study but are not subsequently enrolled in the study. Screening information is recorded in the source documents.

Individuals who do not meet the criteria for participation in this study (screen failure) can be rescreened.

6 Study Interventions and Concomitant Therapy

Study intervention is defined as any investigational intervention(s), marketed product(s), placebo, or medical device(s) intended to be administered to a study participant according to the study protocol.

Note: Vaccines or products administered outside of study protocol are not considered as study interventions and are reported in the case report form (CRF) as reportable medications (see Section 6.8). Study procedures (e.g., blood sampling) are also not considered as study interventions.

6.1 Study Interventions Administered

Table 6.1: Identity of study interventions

Study interventions are described in Table 6.1.

Intervention Name	Fluzone Quadrivalent vaccine, No Preservative (0.5-mL dose), 2021– 2022 formulation	Fluzone High-Dose Quadrivalent vaccine (0.7-mL dose), 2021–2022 formulation	
Use	Other (as indicated in the prescribing material)	Other (as indicated in the prescribing material)	
IMP and NIMP	IMP	IMP	
Туре	Vaccine	Vaccine	
Dose Form	Suspension for injection in a pre-filled syringe	Suspension for injection in a pre-filled syringe	
Unit Dose Strength(s)	 15 μg of HA of each of the following strains per dose: A/Victoria/2570/2019 	 60 μg of HA of each of the following strains per dose: A/Victoria/2570/2019 	
	 (H1N1)pdm09-like virus A/Cambodia/e0826360/2020 (H3N2)-like virus B/Washington/02/2019 (B/Victoria lineage)-like virus B/Phuket/3073/2013 (B Yamagata lineage)-like virus 	 (H1N1)pdm09-like virus A/Cambodia/e0826360/2020 (H3N2)-like virus B/Washington/02/2019 (B/Victoria lineage)-like virus B/Phuket/3073/2013 (B Yamagata lineage)-like virus 	
Excipients/Diluent	Octylphenol ethoxylate (Triton X-100), sodium phosphate-buffered isotonic sodium chloride solution	Octylphenol ethoxylate (Triton X- 100), sodium phosphate-buffered isotonic sodium chloride solution	
Dosage Level	0.5 mL per dose	0.7 mL per dose	

Number of Doses / Dosing Interval	1 or 2 doses 28 (window, 28–35) days apart for children aged 6 months to < 9 years (as per ACIP guidance)	1 dose
Route of Administration	IM injection	IM injection
Site of Administration	Anterolateral muscle of the thigh or the deltoid muscle	Deltoid muscle
Sourcing	Provided by the Sponsor	Provided by the Sponsor
Packaging and Labeling	Fluzone Quadrivalent and Fluzone High-Dose Quadrivalent vaccines will be supplied with their manufacturer's commercial labeling and packaging.	
Current/Former Name(s) or Alias(es)	Not applicable	Not applicable
Batch Number	TBD	TBD
Storage Conditions	Study interventions will be stored in a refrigerator at a temperature ranging from +2°C to +8°C. The study interventions must not be frozen.	

Note: Strains are based on WHO/FDA recommendations for the 2021-2022 NH influenza season

ACIP: Advisory Committee on Immunization Practices; FDA: Food and Drug Administration; HA: hemagglutinin; IM: intramuscular; IMP: Investigational Medicinal Product; NH: Northern Hemisphere; NIMP: Non Investigational Medicinal Product; TBD: to be determined; WHO: World Health Organization

6.2 Preparation/Handling/Storage/Accountability

Detailed guidance and information are provided in the Operating Guidelines.

- 1) The investigator or designee must confirm appropriate temperature conditions have been maintained during transit for all study intervention received and any discrepancies are reported and resolved before use of the study intervention.
- 2) Only participants enrolled in the study may receive study intervention and only authorized site staff may supply or administer study intervention. All study intervention must be stored in a secure, environmentally controlled, and monitored (manual or automated) area in accordance with the labeled storage conditions with access limited to the investigator and authorized site staff.
- 3) The investigator, institution, or the head of the medical institution (where applicable) is responsible for study intervention accountability, reconciliation, and record maintenance (ie, receipt, reconciliation, and final disposition records).

4) Further guidance and information for the final disposition of unused study interventions are provided in the Operating Guidelines.

6.3 Measures to Minimize Bias: Randomization and Blinding

6.3.1 Randomization and Allocation Procedures

Participants will not be randomized. Each participant will be assigned to a vaccine group based on the participant's age at the time of enrollment.

Participant numbers will be 12 digits long, with a 3-digit country identifier, a 4-digit study site identifier, and a 5-digit participant identifier. The 5-digit participant identifier will correspond to the chronological order of enrollment in the site. For example, participant 840000100001 is the first participant enrolled in Site Number 1 (in the United States) and participant 840000200002 is the second participant enrolled in Site Number 2 (in the Unites States).

Participant number should not be reassigned for any reason.

6.3.2 Blinding and Code-breaking Procedures

This is an open-label study.

6.4 Study Intervention Compliance

The following measures will ensure that the study intervention is administered as planned (see Table 6.1), and that any non-compliance is documented so that it can be accounted for in the data analyses:

- All study interventions will be administered by qualified and trained study personnel
- The person in charge of study intervention management at the site will maintain accountability records of study intervention delivery to the study site, study intervention inventory at the site, dose(s) given to each participant, and unused or wasted doses

6.5 Dose Modification

Not applicable.

6.6 Continued Access to Study Intervention After the End of the Study

Not applicable.

6.7 Treatment of Overdose

Since the study intervention is administered by a health care professional, it is unlikely that overdose by injection occurs.

However, in the event of an overdose, the investigator should:

- 1) Contact the Medical Monitor immediately.
- 2) Evaluate the participant to determine, in consultation with the Medical Monitor, whether study intervention should be interrupted
- 3) Closely monitor the participant for any AE/SAE.
- 4) Document the quantity of the excess of the overdose in the source documents.

6.8 Concomitant Therapy

Reportable medications include medications that may affect the interpretation of safety data or may interfere with the development or measurement of the immune response (e.g., the use of immune-suppressors, immune-modulators, or some antibiotics that can affect certain bioassays). Some medications such as steroids can affect both the evaluation of the safety and the immune response to a vaccine.

This may include medications of interest that were started prior to the day of vaccination, and even stopped prior to enrollment if there is a reasonable possibility that they may have an impact on safety and / or immune assessment during study participation.

The following reportable medications are defined:

- Category 2: medications impacting or that may have an impact on the immune response (eg, other vaccines, blood products, antibiotic classes that may interfere with bioassays used by Sanofi Pasteur laboratory or other testing laboratories, systemic steroids/corticosteroids, immune-suppressors, immune-modulators with immunosuppressive properties, anti-proliferative drugs such as DNA synthesis inhibitors
- Category 3: medications impacting or that may have an impact on both the safety and the immune response (eg, systemic steroids/corticosteroids)

Reportable medications will be collected in the CRF from the day of each vaccination to the end of the follow-up period (i.e., from Visit 1 through Visit 2 for participants receiving 1 dose of study vaccine or from Visit 1 through Visit 3 for participants receiving 2 doses of study vaccine).

Dosage and administration route, homeopathic medication, topical and inhaled steroids, as well as topical, ophthalmic, and ear treatments will not be recorded.

Topical analgesics should not be applied at the site of vaccination; however, if they are applied inadvertently to the vaccination site, they should be recorded as a Category 3 medication.

Medications given in response to an AE will be captured in the "Action Taken" section of the AE CRF only. No details will be recorded in the concomitant medication Form of the CRF unless the medication(s) received belongs to one of the pre-listed categories. Medications will not be coded.

6.8.1 Rescue Medicine

Appropriate medical equipment and emergency medications, including epinephrine (1:1000), must be available at the study site in the event of an anaphylactic, vasovagal, or other immediate allergic reaction.

7 Discontinuation of Study Intervention and Participant Discontinuation/Withdrawal

7.1 Discontinuation of Study Intervention

7.1.1 Temporary Contraindications

Should a participant experience one of the conditions listed below, the Investigator will postpone further vaccination until the condition is resolved. Postponement must still be within the timeframe for vaccination indicated in the SoA.

TCI01: Moderate or severe acute illness/infection (according to Investigator judgment) on the day of study intervention administration or febrile illness (temperature $\geq 100.4^{\circ}$ F [38.0°C]).

Temporary intervention discontinuation may be considered by the Investigator because of suspected AEs. For all temporary intervention discontinuations, duration should be recorded by the Investigator in the source documents.

7.1.2 Definitive Contraindications

Participants will permanently discontinue (definitive discontinuation) study intervention for the reasons listed below. These participants must not receive any additional dose of study intervention but should continue to be followed for safety. Additional unscheduled visits may be performed for safety reasons and information will be reported in the source documents.

Should a participant experience at least one of the conditions listed below, the Investigator will discontinue vaccination:

- DCI01: An anaphylactic or other significant allergic reaction to the previous dose of vaccine
- DCI02: Receipt of any non-study vaccine (including a non-study dose of 2021–2022 influenza vaccine), blood-derived immune globulins, blood, or blood-derived products between Visit 1 and Visit 2.
- DCI03: Bleeding disorder, receipt of anticoagulants, or thrombocytopenia, which may be a contraindication for IM vaccination, at the discretion of the Investigator.
- DCI04: Development of any condition that in the opinion of the Investigator would pose a health risk to the participant or could interfere with the evaluation of the study vaccine

(including GBS, clinically significant developmental delay, neurologic disorder, seizure disorder, human immunodeficiency virus infection, hepatitis B, or hepatitis C).

- DCI05: Development of immunodeficiency; or receipt of immunosuppressive therapy such as anti-cancer chemotherapy or radiation therapy; or receipt of long-term systemic corticosteroid therapy (prednisone or equivalent for more than 2 consecutive weeks).
- DCI06: Adverse events that are considered a contraindication for further participation in the study.

In the event of a local or national immunization program with a COVID-19 Vaccine, participants who receive the vaccine mentioned above at any time during the study will not be withdrawn from the study.

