- E13: Receipt of any vaccine in the 30 days preceding the first study intervention administration, or planned receipt of any vaccine before Visit 2 for participants receiving 1 dose of influenza vaccine or Visit 3 for participants receiving 2 doses of influenza vaccine.
- E14: Previous vaccination against influenza (in the 2021-2022 influenza season) with an investigational or marketed vaccine.
- E15: Receipt of blood-derived immune globulins, blood, or blood-derived products in the past 3 months.

Prior/concurrent clinical study experience

E16: Participation at the time of study enrollment (or in the 30 days preceding the first study vaccination) or planned participation during the present study period in another clinical study investigating a vaccine, drug, medical device, or medical procedure.Note: Participants may be considered eligible for enrollment if no intervention for the

^b The components of study interventions are listed in the Prescribing Information for each study vaccine.

^c Chronic illness may include, but is not limited to, cardiac disorders, renal disorders, autoimmune disorders, diabetes, psychomotor diseases, and known congenital or genetic diseases.

other study occurred within the 30 days prior to the first study vaccination and none are planned before the participant would complete safety surveillance for the present study.

Other exclusions

- E17: Deprived of freedom by an administrative or court order, or in an emergency setting, or hospitalized involuntarily.
- E18: Identified as an Investigator or employee of the Investigator or study site with direct involvement in the proposed study or identified as an immediate family member (i.e., parent, spouse, natural or adopted child) or in-law of the Investigator or employee with direct involvement in the proposed study.

Note: Participants enrolled into this study will not be prohibited from donating blood for noninterventional studies or other purposes.

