7.2 Participant Discontinuation/Withdrawal from the Study

- A participant may withdraw from the study at any time at his/her own request, or may be withdrawn at any time at the discretion of the investigator for safety, behavioral, or compliance reasons. This is expected to be uncommon.
- The reason for withdrawal should be clearly documented in the source documents and in the CRF: Adverse Event, Lost to Follow-up, Protocol Deviation, or Withdrawal by Participant or Parent / Legally Acceptable Representative.
- The participant will be permanently discontinued both from the study intervention and from the study at that time.
- If the participant withdraws consent for disclosure of future information, the Sponsor may retain and continue to use any data collected before such a withdrawal of consent.
- If a participant withdraws consent, he/she may request destruction of any biological samples taken (unless local law requires not to destroy them), and the investigator must document this in the site study records.
- Withdrawn participants will not be replaced.

Follow-up of Discontinuations

For participants who have prematurely terminated the study, the site should attempt to contact them and complete all scheduled safety follow-ups, except if they specified that they do not want to be contacted again and it is documented in the source document.

For participants where the reason for early termination is lost to follow-up, the site will not attempt to obtain further safety information. See Section 7.3 for definition of "lost to follow-up".

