9.4.1 General Considerations

Summaries of baseline demographic characteristics of the study participants will be presented. The number of participants enrolled and their age at enrollment (mean, median, and minimum and maximum), sex, race, and ethnic origin will be summarized, along with the number and description of protocol deviations. Listings of participants by age group, sex, vaccine received, and history of vaccination in the previous seasons will be provided.

9.4.2 **Primary Endpoint(s)**

There are no primary endpoints for this study.

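### Does the COVID-19 sentence at the end of Section 7.1.2 contradict DCI02 and leave dose 2 and Blood Sample 2 to the site's choice?

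*Combined protocol and SAP*

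**What the plan says.** Section 7.1.2 lists the conditions that permanently end study vaccination. DCI02 opens with "Receipt of any non-study vaccine", and its window is set by its last words: "blood-derived immune globulins, blood, or blood-derived products between Visit 1 and Visit 2". The item names no exception for a COVID-19 vaccine. The lead-in gives the consequence: such participants "must not receive any additional dose of study intervention but should continue to be followed for safety". The section ends with a sentence on local or national COVID-19 immunization programs: "participants who receive the vaccine mentioned above at any time during the study will not be withdrawn from the study".

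Section 7.2 deals with withdrawal from the study, and its consequence is wider: "The participant will be permanently discontinued both from the study intervention and from the study at that time". Protocol deviation is one of the withdrawal reasons it lists.

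Section 5.2, E13, excludes at entry anyone with a recent vaccine "or planned receipt of any vaccine before Visit 2 for participants receiving 1 dose of influenza vaccine", or before Visit 3 for those receiving two doses.

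Table 1.2 draws the second blood sample at Visit 2 in the one-dose column and at Visit 3 in the two-dose column. Its footnote c ties the visit to the number of doses received. For outputs, Section 9.4.1 states: "Listings of participants by age group, sex, vaccine received, and history of vaccination in the previous seasons will be provided".

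**The concern.** The COVID-19 sentence stands directly beneath the list of definitive contraindications. Nothing in Section 7.1.2 removes anyone from the study, and its lead-in already keeps these participants under safety follow-up. A reader may therefore ask what the sentence is for, unless it is meant to soften DCI02. One site might then withhold dose 2 from a child who had a COVID-19 vaccine after Visit 1, and another might give it.

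The study's only deliverable is a pair of sera, one before vaccination and one after the final dose. Different readings would produce different pairs from similar children. The two-dose column of Table 1.2 shows no blood draw at Visit 2, so a child stopped after dose 1 might seem to have no second sample scheduled. Section 6.8 counts other vaccines among products that may affect the immune response, and no listing in Section 9.4.1 is dedicated to them. In a group of about 30, each child is 1/30 = 3.3% of the panel.

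**Working it through.** The plan has no power calculation and no tested hypothesis (Sections 9.1 and 9.2), so there is no planned figure to reproduce. The check is a side-by-side reading, followed by a count of who can be affected.

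**1. Do DCI02 and the closing sentence conflict?**

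| Text | What it governs | Effect of a COVID-19 vaccine between Visits 1 and 2 |
|---|---|---|
| DCI02 with the 7.1.2 lead-in | Study vaccination | No further study dose; follow-up continues |
| Closing sentence of 7.1.2 | Study participation | Participant is kept in the study |
| Section 7.2 | Withdrawal | Ends vaccination and participation together |

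The first two rows can both be followed. The closing sentence does not mention dose 2 and does not say that DCI02 is set aside. Sections 5 and 8 also rule out waivers.

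**2. Does the sentence have a purpose without being an exception?** Yes. Section 7.2 lets an investigator withdraw a participant for compliance reasons and offers protocol deviation as a recorded reason. The sentence removes that route for COVID-19 vaccination. It also covers the whole study, so it reaches adults, one-dose children and the time after Visit 2, where DCI02 has no dose left to stop.

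**3. Does E13 conflict?** No. E13 is applied at enrollment to vaccines already received or planned. The closing sentence concerns receipt during the study.

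**4. When is Blood Sample 2 drawn if dose 2 is stopped?** Footnote c assigns Visit 2 to recipients of one dose. The objective in Table 3.1 defines the sample as following the final vaccination. A child stopped after dose 1 has received one dose, and that dose was the final one. Both texts therefore lead to Visit 2, though neither names this case.

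**5. Can the affected sera be identified?** Yes. Section 6.8 puts other vaccines in Category 2 and collects them in the CRF from Visit 1 through the participant's last visit. A listing can be made from data already held. The protocol has no sample-validity rule and no per-protocol set. The one analysis set (Section 9.3) needs at least one dose, so a child stopped after dose 1 stays in it.

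**6. How many could be affected?**
- Window: DCI02 matters only until dose 2 is due at Visit 2, which is 28 to 35 days in Table 1.2. The span to Visit 3 is 28 + 28 = 56 to 35 + 35 = 70 days, but its second half lies after dose 2 and is outside DCI02.
- People: Groups 1 and 2 hold about 30 + 30 = 60 children. The share with two doses indicated is not stated, so between 0 and about 60 could lose a dose. In Group 3 the number is 0, because adults have one dose.
- Rate: the documents give no COVID-19 vaccination rate. As an assumption only, take 0% to 20% within the window; zero belongs in the range because E13 removes those who plan a vaccine. The upper limit is 60 × 0.20 = 12 children, reached only if every child needs two doses. If half do, it is 30 × 0.20 = 6.

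**The case for a change.** The best case for a change is that sites do not read protocols as lawyers do. A COVID-19 sentence placed under the contraindication list invites the exception reading, and the bar on waivers means a site in doubt cannot settle the matter itself. Section 7.1.2 promises only safety follow-up to a child stopped after dose 1. Section 8 ties blood draws to the schedule and allows unscheduled ones only for safety or technical reasons. No separate SAP will be written, so Section 9.4 is the only place for a listing of non-study vaccines. Those vaccines can also precede Blood Sample 2 in adults and one-dose children, however Section 7.1.2 is read. The sponsor may test adult sera for breadth of response.

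Part of this stands. The placement is awkward, the exception reading is possible, and the sampling visit for a stopped two-dose child has to be inferred. The rest does not carry a change. A draw at Visit 2 under footnote c is a scheduled draw, so the limit on unscheduled samples does not apply. A listing from Category 2 records would be useful, but it corrects no rule that gives a wrong result, and its absence does not stop anyone from producing it. Visit procedures are detailed in the Operating Guidelines, which were not available for this check, as was any description of the information sent with the sera.

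**Conclusion.** The supposed contradiction does not hold. Read literally, Section 7.1.2 gives one coherent outcome: no further study dose under DCI02, and the participant remains in the study. What is left is loose wording and one sampling point that footnote c and the objective let a reader fill in. It concerns only children with two doses indicated, within a window of 28 to 35 days. Their number is unknown, from 0 to about 60, and those actually vaccinated against COVID-19 in that window would be fewer.

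The study obtains no immunogenicity data itself and has no endpoints or hypotheses, so no estimate or test can be biased by the point. Intercurrent vaccines are on record and can be tabulated. The conclusion rests on the literal text and on sites treating a child stopped after dose 1 as a one-dose recipient for blood sampling. Whether COVID-19 vaccination ought to be an exception to DCI02 is a clinical question for the sponsor, and no view is taken on it here. No change to the plan is needed.
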